#### **4.5.2.6 Secondary Efficacy Endpoints Not Included in the Hierarchy**

Treated target joint bleeds (defined according to Section 2.3.2.4) on emicizumab will be compared with no prophylaxis and will be analyzed using the same methodology as for the primary endpoint (i.e., using the NB regression model or the Van Elteren test).

[REDACTED]

The Haem-A-QoL total score, the EQ-5D-5L index utility score based on the U.K. value set, and the VAS at 24 weeks will be analyzed using the same analysis methodology as the Haem-A-QoL physical health subscore (i.e., via ANOVA).

The same analysis methodology for the intra-patient comparison within Arm D for treated bleeds and all bleeds will be applied for the pooled Arms A and B (episodic patients randomized to emicizumab). Of note: given the small number of NIS episodic patients that were randomized to either Arm A or B, it was considered that a pooled analysis was considered as more appropriate than two separate analyses.

Only a descriptive summary of the Haemo-QoL-SF will be provided because of the small number of adolescents randomized to the study.

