### **2.3.2.4 Treated Target Joint Bleeds**

Target joints are joints into which repeated bleeds occur (i.e.,  $\geq 3$  bleeds into the same joint over the last 24 weeks prior to study entry). The target joints prior to study entry are identified through the eCRF. The bleeds in target joints during the efficacy period are defined by first selecting the bleeds that fulfill the definition of a treated joint bleed and then counting how many of these occurred in a target joint as defined prior to study entry. The locations to be taken into account are shoulder, elbow, wrist, fingers/thumb, hip, knee, ankle, sole/heel, and toes. Left and right sides of the same joint type are considered to be separate joints.

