## **2.4 DETERMINATION OF SAMPLE SIZE**

The sample size for this study is based on clinical rather than statistical considerations, taking into account the limited number of patients with hemophilia A without inhibitors available for participation in clinical studies and in an effort to collect sufficient data to assess the safety and efficacy of emicizumab.

The sample size calculation is based on the evaluation of the primary efficacy endpoint, defined as the number of bleeds over time (i.e., bleed rate) with emicizumab (treatment group,  $\lambda_t$ ) versus no prophylaxis (control group,  $\lambda_c$ ), which are said to follow a negative binomial (NB) distribution. With consideration of enrollment feasibility, a sample size of 75 patients, assuming an allocation ratio of 2:2:1 (30 patients in each randomized treatment group and 15 patients in control group), will achieve a power of more than 90% assuming a mean ABR of 4 and 14 bleeds (with variances = mean  $\times$  10) for the emicizumab treatment and control arms respectively, representing an expected 71% reduction in the ABR compared to the control arm. Initial sample size calculations were performed with East®, Version 6 (Cytel, Cambridge, MA), assuming the patients from each treatment group are followed up to 0.5 units of time (i.e., 24 weeks).

However, the above approach to sample size calculation assumes similar follow-up for each patient. Because this is unlikely to be seen in the study, power was also estimated by simulation to account for different follow-up times among patients. Conducting simulations on the basis of an NB regression model including an offset variable to account for variable follow-up times, with all other assumptions remaining the same as previously described, the sample size is projected to have greater than 90% power at the 2-sided 0.05 level of significance.

The analysis will include all enrolled patients regardless of their length of follow-up. Therefore, to ensure the analysis is based on sufficient follow-up data and with 2:2:1 treatment to control randomization, approximately 34 patients in each randomized

[figure not shown]

emicizumab treatment arm (68 in total) and 17 patients in the control arm (approximately 85 patients in total) will be enrolled.

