### **4.5 EFFICACY ANALYSIS**

The primary and secondary efficacy analyses will be based on the All Patients population (see section [4.2.2](#)).

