#### **4.5.1 Primary Efficacy Endpoint**

The primary efficacy objective is to evaluate the clinical effect of prophylactic emicizumab compared with no prophylaxis on the number of bleeds over time. The definition of a bleed is described in Section [2.3.1](#). The primary endpoint is based on treated bleeds.

The comparison of the number of bleeds over time between the randomized treatment arms will be performed using an NB regression model, which accounts for different follow-up times, with the patient’s number of bleeds as a function of randomization and the time that each patient stays in the study (the length of the efficacy period) included as an offset in the model. The model also includes the number of bleeds ( $<9$  or  $\geq 9$  according to the eCRF data) in the last 24 weeks prior to study entry as a stratification factor. This analytic model estimates the rate ratio,  $\lambda_t/\lambda_c$ , which quantifies the risk of bleeding associated with prophylactic emicizumab ( $\lambda_t$ ) in comparison to no prophylaxis ( $\lambda_c$ ). Statistical significance is controlled at the 2-sided, 0.05 alpha ( $\alpha$ ) level.

Of note, hierarchical testing is used to account for multiple testing and the first test to be included in the hierarchy is the emicizumab 1.5 mg/kg/wk maintenance dose versus

control. The second test will be 3 mg/kg/2wks maintenance dose versus control. A global approach using a model statement (within GENMOD) with a 3-level categorical effect for treatment (“1.5 mg/kg/wk,” “3 mg/kg/2wks,” or “no prophylaxis”) and an appropriate contrast statement will allow both tests to be performed via the following hypothesis

$H_0$  (null hypothesis): Rate Ratio = 1 versus  $H_1$  (alternative hypothesis): Rate Ratio  $\neq$  1.

Statistical significance at the prespecified  $\alpha$  level will be based on a Wald testing procedure. Bleed rates for prophylactic emicizumab and no prophylaxis and the rate ratio will be presented and include 95% CIs.

The number of bleeds can also be annualized for each patient using the following formula:

$$ABR = (\text{Number of bleeds} / \text{Total number of days during the efficacy period}) \times 365.25.$$

Both the model-based method (estimated ABR from the NB model) and the method using the above formula (calculated ABR) will be used to describe the study results.

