#### **4.5.5 Subgroup Analyses**

Comparative subgroup analyses describing the primary endpoint, treated bleed rate, will be conducted for the randomized portion of the study. In addition, estimated ABR including 95% CI will be calculated for all treatment arms in each subgroup. Note, due to the small sample size, all subgroup analyses will be highly sensitive to variability caused by individual patients and need to be interpreted with caution. No p-values will be calculated.

The pre-specified subgroups are:

- Age: < 18, ≥ 18
- Age: < 65, ≥ 65
- Race: Asian, Black or African American, White, Other
- Number of bleeds during 24 weeks prior to study entry: ≤ 9, > 9

- Number of target joints: no target joint, any target joint

Subgroup analyses are subject to having sufficient patients in a subgroup to provide meaningful results.

In addition, region- and/or country-specific analyses will be performed to support regulatory submissions as needed.

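### On the visible SAP text, treated target-joint bleeds are compared in all randomised patients, although those with no target joint at entry can only score zero; an at-risk analysis should be added beside it

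*SAP*

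**What the plan says.** SAP 2.3.2.4 defines the endpoint in two steps: select the treated joint bleeds, "then counting how many of these occurred in a target joint as defined prior to study entry". A target joint is one with at least three bleeds in the 24 weeks before entry, identified from the eCRF.

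SAP 4.5.2.6 says the endpoint "will be compared with no prophylaxis and will be analyzed using the same methodology as for the primary endpoint", that is, by the negative binomial (NB) model or the Van Elteren test. The analysis set comes from SAP 4.5: "The primary and secondary efficacy analyses will be based on the All Patients population". Protocol 6.5 puts the randomised comparisons, primary and secondary, on every randomised patient. Neither text limits this endpoint to patients who have a target joint.

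The plan expects both kinds of patient. SAP 4.5.5 lists the subgroup "Number of target joints: no target joint, any target joint", but only for the treated-bleed rate. Stratification and the NB model use prior bleeds (below 9, or 9 and above) and not target-joint status.

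**The concern.** Eligibility for the randomised arms needs at least five bleeds in 24 weeks, at any site. A patient whose bleeds are spread over several sites qualifies without having a target joint. That patient contributes a zero and full follow-up time to the target-joint model whatever the treatment does. Two things follow.

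- **Precision.** A mixture of patients at risk and patients not at risk is more dispersed than the at-risk group alone. Chance imbalance in target-joint prevalence, with only 17 controls, then moves the estimated rate ratio.
- **Meaning of the rate.** Each arm's target-joint ABR is averaged over people who could not have an event, so it does not describe patients who have target joints.

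The endpoint is a named secondary objective in protocol 2.1.2, with a planned between-arm comparison.

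**Working it through.** **1. The plan's own figure.** SAP 2.4 says that 30 v 15 patients "will achieve a power of more than 90% assuming a mean ABR of 4 and 14 bleeds", "representing an expected 71% reduction in the ABR compared to the control arm", with follow-up of 0.5 time units. It sets the variance at ten times the mean ("with variances = mean" × 10). On the annual scale, variance = m + k·m² = 10m gives k = 9/m: 9/4 = 2.25 on emicizumab and 9/14 = 0.643 on control. The test level is from SAP 4.5.1: "Statistical significance is controlled at the 2-sided, 0.05 alpha".

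Power = Φ(|ln RR|/√V − 1.96), with V = Σ (1/(rate × t) + k)/n over the two arms.

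- Emicizumab: (1/(4 × 0.5) + 2.25)/30 = 0.0917
- Control: (1/(14 × 0.5) + 0.643)/15 = 0.0524
- V = 0.1440, √V = 0.3795, ln(14/4) = 1.2528
- Power = Φ(3.301 − 1.960) = Φ(1.341) = 91.0%

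The stated figure of more than 90% is reproduced. It concerns all treated bleeds; no power is stated for target-joint bleeds.

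**2. What the structural zeros add.** Let a share p be at risk, with NB mean m and dispersion k, and let the rest score zero. The count then has mean pm and variance pm + p(k+1)m² − p²m². Dividing by n(pm)² gives the variance of the log rate in one arm:

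(1/m + k)/(np) + (1 − p)/(p·n)

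The first term is what an analysis of the np patients at risk would have. The second is the addition. Over two arms it is ((1−p)/p)(1/n_A + 1/n_C). With 34 v 17 enrolled, 1/34 + 1/17 = 0.0882.

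| p (assumed) | Added variance | One SD multiplies or divides the rate ratio by |
|---|---|---|
| 0.5 | 1.000 × 0.0882 = 0.088 | exp(0.297) = 1.35 |
| 0.65 | 0.538 × 0.0882 = 0.048 | exp(0.218) = 1.24 |
| 0.8 | 0.250 × 0.0882 = 0.022 | exp(0.149) = 1.16 |

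**3. Dilution of the rate.** The all-patient ABR is p times the at-risk ABR. An at-risk rate of 6 per year shows as 0.65 × 6 = 3.9 at p = 0.65. The factor p has the same expected value in every arm, so it cancels from the rate ratio.

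**4. Power, conditional on assumptions.** The documents do not give p, the control target-joint rate, the target-joint effect or the target-joint dispersion. Assume the planning effect (RR 4/14 = 0.286) and planning dispersions carry over, t = 24 weeks (0.460 year), and a control rate of 7 per year among patients at risk. At p = 0.5:

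- At risk: V = (1/(2 × 0.460) + 2.25)/17 + (1/(7 × 0.460) + 0.643)/8.5 = 0.308; power Φ(2.256 − 1.960) = 62%
- All randomised: V = 0.308 + 0.088 = 0.397; power Φ(1.989 − 1.960) = 51%

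| p | All randomised | At risk only | Gain (from unrounded values) |
|---|---|---|---|
| 0.4 | 41% | 52% | 11 |
| 0.5 | 51% | 62% | 10 |
| 0.6 | 61% | 70% | 9 |
| 0.7 | 69% | 76% | 7 |
| 0.8 | 77% | 81% | 4 |
| 0.9 | 84% | 86% | 2 |

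Over control rates of 3 to 14 per year and p from 0.4 to 0.9, the closed-form gain is 2 to 14 points.

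**5. Simulation.** At RR 0.286, rates of 4 to 10 per year and p of 0.4 to 0.8, fitting the three-arm NB model with a common dispersion gave gains of about 5 to 22 points. With RR 0.05 to 0.10 and p of at least 0.65, the gain was about 0 to 3 points. Simulated type I error was about 0.02 to 0.06 for the all-randomised analysis. For the at-risk analysis it was about 0.03 to 0.05 with planning dispersions, but mostly 0.05 to 0.08 (highest 0.095) with a common k of 1. These runs omitted the prior-bleed covariate and used 24 weeks of follow-up in every arm. Fitted this way, the primary design itself gave about 87%, a little below the closed form.

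**The case against.** **The all-randomised analysis is valid.** It follows intention to treat and protocol 6.5. A reader might infer that the zeros pull the rate ratio towards 1; they do not, because they scale both arms equally in expectation. Chance imbalance in prevalence is already reflected in the standard error. This stands: the loss is of precision and interpretability, not validity.

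**Little hangs on it.** SAP 4.5.2.6 places the endpoint outside the hierarchy and no power is claimed for it. This stands too.

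**The cost may be near zero.** Protocol 3.3.1, Table 1 reports mean ABR reductions of 95.3% and 96.4% at the two higher early-phase doses, a rate ratio near 0.05 for bleeds overall. If target-joint bleeds respond similarly and most patients have a target joint, power is close to 100% either way. This limits the power argument; the dilution of the ABR remains.

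**The model's covariate may help.** Having 9 or more prior bleeds plausibly tracks target-joint status. With an assumed prevalence of 40% v 90% by stratum, one simulated gain fell from about 12 to 9 points, a difference within simulation error.

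**The public text is incomplete.** Redacted text follows the target-joint sentence in SAP 4.5.2.6, and SAP 4.2.8 is redacted. Either could hold a restriction, so the point is confined to what is visible.

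**Conclusion.** On the visible text, patients who cannot have a target-joint bleed are analysed as if they could. The extra variance, ((1−p)/p)(1/n_A + 1/n_C), and the dilution of each arm's ABR by p follow from the definition; only p has to be assumed.

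The power cost is conditional. A reader might take one scenario as the answer: with a control rate of 6 per year, RR 0.3, planning dispersions and 24 to 52 weeks of follow-up in Arms A and B, simulation gives 41% to 55% at p = 0.5, 52% to 63% at p = 0.65 and 68% to 74% at p = 0.8, a gain of 6 to 14 points. The documents do not support that as a fixed figure, since they supply neither the prevalence nor the target-joint rate or effect. The defensible statement is about 2 to 14 points by closed form at the planning effect, up to about 20 in simulation, and about 0 to 3 if the effect is very large and p is at least 0.65. Part of the larger simulated gains with k = 1 reflects a mildly anti-conservative Wald test.

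This is a worthwhile, inexpensive improvement to a supportive endpoint. It does not threaten any confirmatory conclusion.

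**What to change.** In SAP 4.5.2.6, add an analysis of treated target-joint bleeds in randomised patients with at least one target joint at entry. Use the same NB or Van Elteren method, and report the number at risk and the at-risk ABR for each arm. Present it beside the all-randomised analysis and not in its place: protocol 6.5 requires the latter, and replacing it would be a departure from the protocol. Because the subset is defined at baseline, the comparison remains a randomised one. If a restriction already exists in redacted text, stating the analysis set in this section is enough.

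The cost is a short SAP addition. Target joints are already recorded on the eCRF, and the any/none flag is already needed for SAP 4.5.5; alpha allocation does not change. The downside is a small control group, 17 × 0.5 = 8.5 to 17 × 0.8 = 13.6, so about 8 to 14 patients at 50 to 80% prevalence. In a group that small the Wald test may be slightly anti-conservative, and the output should say so.

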2.1.2 Secondary Efficacy Objectives

The secondary efficacy objectives for this study are as follows:

- To evaluate the efficacy of prophylactic emicizumab (in each individual emicizumab arm) on the basis of the following endpoint:

Change in the number of bleeds over time compared with the patient's historical bleed rate *

- To evaluate the efficacy of prophylactic emicizumab administered at 1.5 mg/kg/wk or 3 mg/kg/2wks subcutaneously compared with no prophylaxis for patients previously treated with episodic FVIII on the basis of the following endpoints:
 - All bleeds over time
 - Spontaneous bleeds over time (spontaneous bleed rate)
 - Joint bleeds over time
 - Target joint bleeds over time (target joints are defined as joints with ≥ 3 bleeds occurring in the same joint over the last 24 weeks prior to study entry)
 - HRQoL of patients according to Haem-A-QoL (aged ≥ 18) or Haemo-QoL-Short Form (aged 12–17) scores after 24 weeks
 - Health status of patients according to European Quality of Life 5-Dimensions-5 Levels Questionnaire (EQ-5D-5L) scores after 24 weeks
- To evaluate the efficacy of prophylactic emicizumab administered at 1.5 mg/kg/wk subcutaneously for patients previously treated with prophylactic FVIII on the basis of the following endpoint:
 - Maintaining adequate control of bleeding by evaluation of the bleed rate *

* Analyses will be performed for treated bleeds and all bleeds.

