3.3.2 Rationale for Patient Population

As described in Section 3.3, patients with hemophilia A who were treated with episodic FVIII prior to study entry will comprise the primary population for this Phase III study of prophylactic emicizumab compared with no prophylaxis in investigating the efficacy, safety, and PK of emicizumab.

Although the severity of a patient's hemophilia A is directly related to the endogenous FVIII activity, inter-patient variability may exist based on level of physical activity, bleeding history and other features. Therefore, patients previously treated with episodic FVIII will be required to have at least 5 bleeds in the last 24 weeks prior to study entry to be eligible for enrollment in the randomized portion of Study BH30071. This is to select a group of patients with hemophilia A without inhibitors who have a high, unmet medical need and to enable detection of a clinically and statistically significant difference in bleed rates in this population. Similar approaches were previously employed (Manco-Johnson et al. 2013; Mahlangu et al. 2014).

Patients who were treated with prophylactic FVIII prior to enrollment are included in a separate arm in Study BH30071, as combining them with those previously treated with episodic FVIII would introduce significant heterogeneity in baseline bleed rates and goals of care.

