3.3.3 Rationale for Control Group

The control group for the primary efficacy endpoint will be a concurrent, no prophylaxis “usual care” arm, to which patients who were on episodic FVIII prior to study entry will be randomized (2:2:1 prophylactic emicizumab 1.5 mg/kg/wk:prophylactic emicizumab 3 mg/kg/2wks:no prophylaxis), which will enable an inter-patient comparison of the

treatment and control groups. All patients, whether assigned to receive prophylactic emicizumab or no prophylaxis, will continue to receive FVIII on an episodic basis for the treatment of breakthrough bleeds during the study. Specific doses of FVIII will not be mandated in the study, but investigators should review with patients the dose to be used to treat breakthrough bleeds. Breakthrough bleeds should be treated with the lowest FVIII dose expected to achieve hemostasis, which may be lower than the patients' prior FVIII dose.

A second comparison will be an individual patient's bleed rate calculated over the 24 weeks prior to study entry, from the medical record and/or Study BH29768. This will enable intra-patient analyses of bleed rates to be performed.

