4.1.1 Inclusion Criteria

Patients must meet the following criteria for study entry:

- Signed Informed Consent Form by the patient or a legal guardian
- Able to comply with the study protocol, in the investigator's judgment

- Willingness and ability to comply with scheduled visits, treatment plans, laboratory tests, and other study procedures, including the completion of patient-reported outcome questionnaires and bleed and medication diary through the use of an electronic device
- Aged 12 years or older at the time of informed consent
- Body weight ≥ 40 kg at the time of screening
- Diagnosis of severe congenital hemophilia A (intrinsic FVIII level $< 1\%$)
- A negative test for inhibitor (i.e., < 0.6 BU) within 8 weeks of enrollment
- No documented inhibitor (i.e., < 0.6 BU), FVIII half-life < 6 hours, or FVIII recovery $< 66\%$ in the last 5 years
- Patients who completed successful immune tolerance induction (ITI) at least 5 years before screening are eligible, provided they have had no evidence of inhibitor recurrence (permanent or temporary) as may be indicated by detection of an inhibitor, FVIII half-life < 6 hours, or FVIII recovery $< 66\%$ since completing ITI (Antun et al. 2015).
- Documentation of the details of prophylactic or episodic FVIII treatment and of number of bleeding episodes for at least the last 24 weeks
- For patients on no prophylaxis (episodic treatment) pre-study, ≥ 5 bleeds in the last 24 weeks prior to study entry
- Patients who were on FVIII prophylaxis for at least the last 24 weeks, can be enrolled regardless of the number of bleeds during this period. Eligibility will be based on investigator's attestation of adequate prophylaxis regimen.
- At least 40 patients who were on FVIII prophylaxis pre-enrollment will have been enrolled for a minimum of 24 weeks in Study BH29768 (non-interventional)
- Adequate hematologic function, defined as platelet count $\geq 100,000/\mu\text{L}$ and hemoglobin ≥ 8 g/dL (4.97 mmol/L) at the time of screening
- Adequate hepatic function, defined as total bilirubin $\leq 1.5 \times$ the upper limit of normal (ULN) (excluding Gilbert's syndrome) and both AST and ALT $\leq 3 \times$ ULN at the time of screening; no clinical signs or known laboratory/radiographic evidence consistent with cirrhosis
- Adequate renal function, defined as serum creatinine $\leq 2.5 \times$ ULN and creatinine clearance by Cockcroft-Gault formula ≥ 30 mL/min

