### **2.3.2.5 Intra-Patient Comparison**

In the intra-patient comparison (on All Bleeds and on Treated Bleeds as defined in Section 2.3.2.1 and Section 2.3.2.2, respectively), only patients who participated in NIS BH29768 are included. This is because it is possible to apply the detailed bleed definitions only if the data are collected with the same granularity for both time periods. Of note, for some episodic patients who participated in NIS BH29768, the total time in that study prior to enrollment in Study BH30071 may be less than 24 weeks.

The efficacy period in NIS BH29768 is defined as the time from the first entry on the electronic, handheld device or site data entry system to the day the patient completed the study, which may occur between 1 day and a few days prior to

enrollment/randomization in Study BH30071. Usually, the date of the first BMQ entry in NIS BH29768 is the date the Training Module on the electronic, handheld device is completed. The end of the efficacy period in NIS BH29768 is defined as the date of withdrawal or date of study completion or on the day of the clinical cutoff, whichever occurs earlier.

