## **4. STATISTICAL METHODS**

### **4.1 OUTPUT LAYOUTS**

The key output layouts are designed to address the study objectives in a flexible manner and provide an overall view of the efficacy and safety of emicizumab. In particular, patients in Arm C are allowed to switch to receive emicizumab after the first 24 weeks in the study, yielding two “study periods” (i.e., when they receive no prophylaxis for the first 24 weeks [no prophylaxis period, designated Arm Ccontrol] and emicizumab prophylaxis thereafter [emicizumab period, designated Arm Cemi]). These two periods are analyzed

separately, and either period can be displayed on outputs together with the other treatment arms.

The four key output layouts are:

- **Randomized patients:** comparison of either emicizumab 1.5 mg/kg/wk (Arm A) versus no prophylaxis (control arm [Arm Ccontrol] prior to switch to emicizumab) or emicizumab 3 mg/kg/2wks (Arm B) versus no prophylaxis (Arm Ccontrol), within a single output produced for all comparisons involving arms A, B, and C prior to switch (Arm A versus Arm Ccontrol and Arm B versus Arm Ccontrol); these outputs form the core set of the efficacy comparisons and will be supported by a corresponding safety analysis
- **All patients:** these outputs will be used to describe the baseline characteristics and study conduct
- **All emicizumab patients:** these outputs will provide an overall view of all data collected under emicizumab prophylaxis (including control arm patients after switch [Arm Cemi]) and will include analyses of safety and descriptive efficacy
- **Intra-patient comparisons:** Arm D is displayed separately with its own historical control (for Arms A and B, the patients are combined; see Section 4.5.2.6); for evaluations of the secondary endpoint with intra-patient comparisons, only patients who participated in the NIS BH29768 are included

Of note, patients may be allowed to up-titrate their emicizumab dose as described in Section 2. The data under the new, higher dose are analyzed and reported separately. Additional summaries will be produced for key safety and exposure on all data (i.e., data before and after up-titration). Note, with longer follow-up or in case up-titration occurs more frequently than expected, outputs on all data may form the core analysis and additional summaries will be produced by dose.

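### The pooled Arm A and B before-after comparison takes its baseline from the window in which patients were selected for at least 5 bleeds, so regression to the mean inflates the reduction, and no Arm C change is shown beside it

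*SAP*

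**What the plan says.** Protocol 2.1.2 lists as its first secondary efficacy objective, for each individual emicizumab arm: "Change in the number of bleeds over time compared with the patient's historical bleed rate". Protocol 3.3.3 describes the baseline: "A second comparison will be an individual patient's bleed rate calculated over the 24 weeks prior to study entry", taken from the medical record and/or the NIS.

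The SAP narrows the data source. For these evaluations, "only patients who participated in the NIS BH29768 are included" (SAP 4.1). SAP 2.3.2.5 ends the NIS period on the day the patient completed that study, "which may occur between 1 day and a few days prior to" enrolment or randomization. It adds that for some episodic patients "the total time in that study prior to enrollment in Study BH30071 may be less than 24 weeks".

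Previously episodic patients "will be required to have at least 5 bleeds in the last 24 weeks prior to study entry" (Protocol 3.3.2; also the inclusion criteria in 4.1.1). Arm D has no minimum bleed count.

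SAP 4.5.2.4 analyses Arm D with the primary negative binomial (NB) model plus a REPEATED statement. SAP 4.5.2.6 says this "will be applied for the pooled Arms A and B (episodic patients randomized to emicizumab"), and explains the pooling by the small number of NIS episodic patients. SAP 4.5.4 adds a version split by arm. No readable part of either document mentions regression to the mean.

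**The concern.** The patient's count in the 24 weeks before entry has to be high for the patient to be in the trial. If that stretch of time is also the baseline, part of the later fall is the count returning to the patient's usual rate. A before-after ratio cannot separate this from a drug effect. The method suits Arm D, which was not selected on bleeds. It does not carry over unchanged to Arms A and B, which were.

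Nothing planned removes the problem. Splitting A from B leaves both halves selected in the same way. The stratification factor (fewer than 9 versus 9 or more bleeds) is itself defined on the 24 weeks before entry.

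At stake is how the first-listed secondary objective is reported for previously episodic patients. The reduction and any p-value could be read as a drug effect when part of both comes from selection.

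**Working it through.** **Anchor to the plan.** The SAP gives no figure for this comparison. The nearest is its power statement (SAP 2.4): ABR 4 versus 14, variance 10 times the mean, 30 versus 15 patients, 0.5 years, power above 90%. On the annual scale the NB dispersion is k = 9/mean, so 2.25 for emicizumab and 0.643 for control. Var(log ratio) = (1/(4×0.5) + 2.25)/30 + (1/(14×0.5) + 0.643)/15 = 0.0917 + 0.0524 = 0.144. Then ln(3.5)/√0.144 = 1.253/0.380 = 3.30, and 3.30 − 1.96 = 1.34, which gives 91% power. The figure is reproduced, so the annual reading of the variance is used below.

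**Model.** A patient's rate λ is gamma with mean μ and dispersion k. The 24-week count N is Poisson(λt), with t = 168/365.25 = 0.460. Patients with N ≥ 5 are kept, the NIS period is set equal to the window, and there is no drug effect.
- Historical rate = E[N | N≥5]/t
- Later rate = (1/k + E[N | N≥5]) / (1/(kμ) + t)

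Example with μ = 14 and k = 0.643: E[N | N≥5] = 10.22, so the historical rate is 10.22/0.460 = 22.2 per year. The later rate is (1.556 + 10.22)/(0.111 + 0.460) = 20.6. The ratio is 0.928, a 7% fall with no treatment. A true ratio of 4/14 = 0.286 then appears as 0.286 × 0.928 = 0.265, so a 71.4% reduction reads as 73.5%.

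**Grid over the source population (before selection).**

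| Mean ABR | Variance/mean | Historical | Later | Ratio | True 71.4% reads as |
|---|---|---|---|---|---|
| 10 | 3 | 15.7 | 12.7 | 0.811 | 76.8% |
| 10 | 10 | 20.3 | 18.3 | 0.901 | 74.3% |
| 14 | 3 | 17.7 | 15.8 | 0.890 | 74.6% |
| 14 | 10 | 22.2 | 20.6 | 0.928 | 73.5% |
| 18 | 3 | 20.3 | 19.1 | 0.941 | 73.1% |
| 18 | 10 | 24.4 | 23.2 | 0.949 | 72.9% |

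**Enrolled patients with a true ABR of 14.** This is the more natural reading of the planning control rate, because the control arm consists of selected patients. For k from 0.3 to 2.0 the historical rate is 16.6 to 17.0 and the ratio 0.842 to 0.825. With variance 3 times the source mean the ratio is 0.849. The fall is thus about 15-18%, and a true 71.4% reads as about 76%.

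**Length of the NIS period (simulated, mean 14, k = 0.643).** The ratio is 0.930 at 8 weeks, 0.928 at 12, 0.927 at 24 and 0.952 at 36. A short NIS period inside the window is inflated just as much. Only time before the window dilutes the effect: (24×22.2 + 12×20.6)/36 = 21.7, and 20.6/21.7 = 0.95.

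**If patients' own rates drift (assumption).** With mean 14 and a 24-week NIS period, letting 25% or 50% of the overdispersion be change within patients moves the ratio to 0.854 or 0.775. Constant rates are therefore the mild case.

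**The test.** With no drug effect, mean 14, k = 0.643 and two 24-week periods, a paired robust Wald test at nominal 5% rejects in about 14% of trials with 15 patients and 18% with 30 (both numbers assumed). Some of this is small-sample behaviour: the same simulation without selection rejects in about 10% and 7%.

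**The case against.** The strongest reply is that the question is already answered without this bias. A versus C and B versus C compare randomized patients who all met the same bleed threshold. They carry both primary tests and eight of the ten hierarchical secondary tests. Protocol 3.3 itself calls the randomized design better than a historical control, and the SAP keeps the A+B comparison out of the hierarchy while Arm D's is in it. All of this stands, and it limits the point to a supportive analysis.

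The model also takes the qualifying count to be the NIS diary count. Protocol 3.1 says the NIS helps identify and confirm candidates. However, Protocol 4.5.2 records pre-entry bleeds under medical history. If the two counts are only partly related, the inflation is smaller than shown.

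Four stronger readings might be inferred, and the documents do not support them.
- That Arm C's data go unused. Its control period is the randomized comparator, and its emicizumab period is summarized with all emicizumab patients. Only a paired Arm C contrast is missing from the readable text, and a passage of SAP 4.5.2.6 is redacted.
- That the SAP credits the whole fall to emicizumab. It names a model and makes no attribution.
- That the whole estimate must favour the drug. Selection pushes that way, but the emicizumab period starts at the first dose and includes the loading weeks, which pull the other way.
- That partial overlap always shrinks the bias. The NIS-length check shows otherwise.

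A correction from Arm C would also be noisy. If A+B holds 15 to 30 NIS patients (assumed), 2:2:1 randomization implies about 15/4 ≈ 4 to 30/4 ≈ 8 in Arm C. Around a true ratio of 0.93, the simulated central 95% range is 0.56 to 1.40 with 4 patients and 0.66 to 1.24 with 8, and about 30% of trials show no fall at all. This is a reason to report the correction with its interval and not to rely on it alone.

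**Conclusion.** The concern holds for one analysis: the non-hierarchical A+B comparison with the NIS baseline. The overlap follows from the text, and the selection component inflates the reduction. With constant patient rates and the NIS count equal to the qualifying count, the spurious fall is about 5-19% across the grid, and about 15-18% if enrolled patients truly bleed at 14 per year. A true 71% reduction reads as about 73-77%. That adds some 2 to 5 points to a large effect and does not overturn it.

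The size is a range because the documents do not give NIS durations, NIS numbers by arm, or the within-patient share of the variance. A reader might infer that the primary result or Arm D is compromised. Neither is affected by this selection: the three randomized arms were selected alike, and Arm D had no bleed threshold.

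Separately, the scope is inconsistent. Protocol 6.5.2 extends the historical comparison to every patient, Protocol 2.1.2 limits it to each emicizumab arm, and the SAP's readable text names only Arm D and Arms A and B.

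**What to change.** In SAP 4.5.2.6, keep the A+B NIS comparison, but label it descriptive and subject to regression to the mean. Report beside it, with the same NB model and REPEATED statement:
1. The NIS-to-control change in Arm C patients who were in the NIS, and the A+B change divided by it. In the worked example 0.265/0.928 returns 0.286.
2. As support only, the change from control period to emicizumab period in Arm C patients who switched. Its baseline starts after selection. It should not lead, because it is not a comparison with the historical rate.

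Reconcile the scope in Protocol 6.5.2 with the SAP.

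The cost is SAP wording and a little extra modelling on data already collected. The downsides are that the Arm C NIS subset is likely very small, so the ratio will be imprecise, and that the switch contrast covers only the 3 mg/kg/2wks regimen, with little emicizumab follow-up for late switchers at the primary cutoff.
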